1.0 Objectives**1.1 Specific Aims**

- Aim 1: Determine the feasibility (e.g., recruitment, level of participation) and acceptability (treatment satisfaction) of bright white light (BWL) as an intervention for cancer-related cognitive impairments (CRCI) in autologous and allogeneic hematopoietic stem cell transplant (HSCT) survivors.
- Aim 2: Assess the preliminary efficacy of BWL compared to dim red light (DRL) on cognitive functioning in preparation for a large-scale randomized controlled trial.
- Exploratory Aim 1: Investigate the possible mediating effect of circadian activity rhythms (CARs) and sleep quality on cognitive functioning.
- Exploratory Aim 2: Explore a) whether BWL compared with DRL affects biological (inflammatory immune response) variables; and b) whether the effects of BWL compared to DRL on cognitive functioning are mediated by biological factors (i.e., inflammatory immune response).

1.2 Hypotheses

- Hypothesis 1: BWL treatment will be feasible and acceptable in autologous and allogeneic HSCT survivors.
- Hypothesis 2: Auto-HSCT and allo-HSCT survivors receiving BWL will have greater improvement in cognitive functioning than those receiving DRL.
- Hypothesis 3: The relationship between BWL and CRCI will be mediated by CAR and sleep.

2.0 Background**2.1 Relevant prior experience and gaps in current knowledge.**

Cancer-related cognitive impairment (CRCI) due to cancer and/or its treatment has been well-documented.^{24, 25} Hematopoietic stem cell transplant (HSCT) patients often experience CRCI before and after completion of transplantation.^{10-14, 16, 26} This pattern of CRCI is not surprising because, in addition to aggressive treatment during the transplantation regimen, many patients undergo radiation, chemotherapy, or biologic therapies prior to their transplant. Such therapies have been linked to neurological changes in the brain, including white matter abnormalities, atrophy, and electroencephalogram abnormalities.^{27, 28} Immediately after HSCT, there is generalized decline in cognitive functioning with subsequent recovery for most survivors by one year post-transplant. However, recovery does not mean a return to “normal.” Between 15 and 32% of these individuals demonstrate CRCI prior to transplant.¹⁵ Additionally, 54% of patients not impaired before transplant have impairments at one year post-HSCT,¹⁵ and 41.5% experience cognitive impairments 5 years post-HSCT, particularly in motor coordination, speed, and memory.¹⁰ In a recent review and meta-analysis of changes in cognition in HSCT patients, 12 to 89% experienced deficits before HSCT and such symptoms were likely to persist post-HSCT.²⁹ In another recent study of autologous HSCT patients, nearly half showed impairments in learning/memory or executive function after induction therapy. Although the impact of CRCI on

PROTOCOL TITLE: Treating cognitive impairments in cancer patients via systematic light exposure

quality of life can be significant,¹⁷ there is a dearth of research on interventions to treat CRCI.^{18, 19}

2.3 Significance of the research

Systematic Bright White Light Exposure

One novel non-pharmacologic approach for treating CRCI may be systematic bright white light (BWL) exposure. Bright light has been used to reduce depression, fatigue, and sleep disorders in other groups (e.g., seasonal affective disorder, breast cancer, traumatic brain injury)^{33,34-36} and has been found to have beneficial effects on cognitive functions in non-cancer populations.³⁷⁻⁴³ Indeed, a recent *Nature Reviews* article highlighted the important influence of ambient and systematic light on cognitive functioning.¹ It has yet to be tested for the treatment of CRCI. See Figure 1 for hypothesized direct and indirect impact of BWL on cognition.

Direct Effect of Light on Cognition: Light affects cognition directly through a non-image forming (retinal photoreceptor) system.²² Neuroimaging research shows that light can modulate a) subcortical structures related to alertness, b) limbic areas related to mood and memory, and c) cortical areas related to higher level cognition.^{22, 23} In other words, light impacts brain structures that are responsible for low- to high-level cognitive functions – from basic attention to executive functioning. Indeed, research shows that bright light exposure exerts beneficial effects on cognition.³⁷⁻⁴³ Light exposure research has been undertaken in healthy populations and clinical

PROTOCOL TITLE: Treating cognitive impairments in cancer patients via systematic light exposure

populations with cognitive deficits similar to those found in cancer patients. In one study, healthy participants given increased light exposure exhibited greater improvements in cognition (alertness, psychomotor vigilance, or neuropsychological test performance) than those in a dim light therapy comparison group or matched control group.³⁷⁻⁴¹ Bright light exposure studies in dementia patients has shown that patients exposed to bright light showed improvements in cognition but not when exposed to dim light.^{42,43} However, the quality of this research has been marred by small sample sizes⁴⁴ and the use of a gross screening measure (i.e., Mini-Mental State Examination scores). Promising research has been undertaken in patients with mild brain injury with the range and severity of cognitive impairments more similar to that of HSCT survivors. Preliminary data from 18 participants indicated that 30 minutes of increased light exposure each morning for 6 weeks resulted in marked improvement in cognitive functioning (i.e., attention, processing speed, memory, and executive functioning). In addition, daytime sleepiness decreased and mood improved (all $p < .05$).³³ These studies suggest that bright light exposure may improve cognitive functioning in lower-level (e.g., attention) to higher-level domains (e.g., memory). Given that CRCI in HSCT patients also affects lower-level to higher-level skills, BWL may be an effective cognitive intervention for HSCT patients. In cancer patients, BWL has also shown promise in treating CRCI. Co-mentor [name] and colleagues pilot-tested a BWL regimen with breast cancer patients undergoing chemotherapy. Ten patients were randomized to BWL or a comparison DRL condition. Overall cognitive functioning and CAR improved in the BWL group only (see C.1. Preliminary Research). The results in this area of research are preliminary, underscoring the need for an examination of bright light exposure as a treatment for cognitive impairment. Individuals with CRCI represent a worthy target for this examination due to the broad nature of their deficits and their tendency to also suffer from sleep problems and fatigue (discussed below), thus, making them more amenable to this form of intervention.

Indirect Effects of Light on Cognition: Light may also affect cognition indirectly through several mechanisms that have been proposed to contribute to CRCI. An examination of all of the possible mechanisms is beyond the scope of this proposal. Mechanisms to be examined in this proposal are discussed below.

Psychological correlates of CRCI: Fatigue is a potential psychological correlate of CRCI and mechanism through which light affects cognition. While it is well-established that fatigue is related to cognitive functioning in both healthy and non-cancer populations,^{51, 51-53} the few studies with cancer patients have yielded no association.^{54,55} Our pilot work indicates BWL may reduce fatigue in cancer patients³⁶ raising the possibility that BWL affects CRCI via its effects on fatigue. Depressed mood is also a potential psychological correlate of CRCI and mechanism through which light affects cognition. Depressed mood is a well-established correlate of cognitive impairment in non-cancer populations,⁴⁵⁻⁴⁷ but the few existing studies in cancer populations have yielded mixed findings.⁴⁸⁻⁵⁰ Our pilot work indicates BWL reduces depressed mood in cancer patients (see C.1. Preliminary Studies) raising the possibility that BWL may affect CRCI via its effects on depressed mood.

Circadian Activity Rhythms (Chronobiological Variable) and Sleep: Another proposed mechanism is circadian activity rhythms (CARs). CARs serve the function of preparing the body and mind for restful sleep at some times of the day and for active wakefulness at others.⁵⁶ CARs are biological cycles that are slightly longer than 24 hours and are entrained to the 24 hour day by environmental Zeitgebers (time cue) such as bright light.⁵⁷ Several studies have observed dysfunction in CARs among cancer patients.⁵⁸⁻⁶⁰ For example, [name] (co-mentor) and

PROTOCOL TITLE: Treating cognitive impairments in cancer patients via systematic light exposure

colleagues showed that CAR variables including amplitude, mesor, and rhythmicity were significantly impaired during the course of chemotherapy in breast cancer patients.⁶¹ Sleep is another proposed mechanism as sleep problems are often reported by HSCT patients.⁶² Dysfunction of CARs and sleep affects several psychological and physiological processes⁶³ including multiple domains of cognitive functioning.⁶⁴⁻⁶⁸ Effects on cognition range from low- to high-level functions including attention, working memory, motor, verbal functions, and executive functions – areas also affected in many HSCT patients. BWL has been found by co-mentors and others to improve CARs and sleep,^{33, 69, 36, 70, 71} including in cancer patients.⁷¹ By extension, BWL may improve cognitive functioning through its effects on sleep and CARs.³⁹

Inflammatory Immune Response (Biological Variable): Another proposed mechanism is the inflammatory immune response. Evidence suggests that inflammatory mechanisms within the central nervous system contribute to cognitive impairment (including CRCI) via cytokine-mediated interactions between neurons and glial cells.⁷²⁷³ Cytokines play an important role in normal central nervous system functioning⁷² including modulation of neuronal and glial cell function; neural repair; and impact the metabolism of neurotransmitters important for cognitive functioning.⁷⁴ Despite the blood-brain barrier's protective mechanism, there is significant communication between peripheral cytokines and cytokines in the brain.⁷² Certain cytokine levels are likely to be elevated in patients prior to and after autologous HSCT and are thought to be related to the cancer itself and/or tissue damage from conditioning therapy.⁷⁵⁻⁷⁷ It is likely that excessive cancer- and treatment-derived inflammation leads to cognitive impairment via effects on central nervous system pathways and dysregulation of the hypothalamic-pituitary axis (HPA).⁷⁸ Connections between peripheral cytokine activation and cognitive function have been shown in animal and human studies of inflammatory cytokine activation.^{54, 79-81} One animal study found that mice who received an injection of a cytokine-producing substance exhibited working memory impairment but mice with interleukin (IL)-6 knocked out did not exhibit impairment.⁸¹ Additionally, IL-1 β , IL-6, and tumor necrosis factor (TNF)- α are reported to induce synthesis of C-reactive protein (CRP)⁸² that has been associated with cognitive impairment.⁸³ IL-10 has also been found to be critical for maintaining normal neuroimmune communication during infection thus protecting hippocampal-dependent working memory.⁸⁴ A study of healthy young men with low-grade inflammation induced by administration of an endotoxin showed a negative association between circulating IL-6 and memory functions.⁸⁵ Among cancer patients, one study showed that a significant proportion of acute myelogenous leukemia and myelodysplastic syndrome patients had impaired cognitive function prior to chemotherapy treatment.⁵⁴ IL-1, IL-1 receptor antagonist (IL1RA), IL-6, IL-8, and TNF- α levels were elevated compared with laboratory normative controls and elevated IL-1 was associated with poorer executive function. In a study of post-chemotherapy treated breast cancer patients, higher soluble receptors for tumor necrosis factor type II (sTNF-RII) levels were associated with increased memory complaints and this relationship was evident longitudinally.⁸⁶ In summary, animal and human studies highlight the importance of the inflammatory immune response as a potential mechanism that underlies cognitive changes in cancer patients, particularly with respect to IL-1RA, sTNF-RII (surrogate markers for IL-1 and TNF- α activity that are likely to be measurable in HSCT patients), IL-6, IL-8, IL-10, and CRP levels. BWL has been found to normalize HPA axis function⁸⁷ raising the possibility that BWL may affect cognitive functioning via proinflammatory cytokine activity's normalizing effects on the HPA axis.

Summary: CRCI is a major clinical problem affecting a significant proportion of HSCT survivors.^{10, 15} This study will examine the effects of BWL on CRCI in autologous and

PROTOCOL TITLE: Treating cognitive impairments in cancer patients via systematic light exposure

allogeneic HSCT patients – an intervention associated with improved cognitive functioning^{42, 43} ([name]'s pilot work). HSCT patients with CRCI are a worthy target for this intervention due to the broad nature of their deficits and tendency to also have sleep problems and fatigue.

3.0 Inclusion and Exclusion Criteria

3.1 How individuals will be screened for eligibility

The first part of the screening interview can be conducted by phone and internet. It includes questions based on inclusion/exclusion criteria. Participants who meet criteria for entry into the study will be randomly assigned to BWL or DRL. Participants who are ineligible or decline participation will be thanked for their time and informed that they have completed the study.

3.2 Criteria that define who will be included or excluded in final study sample

Eighty autologous and allogeneic HSCT survivors will be recruited at Northwestern University, Feinberg School of Medicine, Department of Medical Social Sciences from Northwestern Memorial Hospital (NMH) and Robert H. Lurie Comprehensive Cancer Center (RHLCCC).

In order to qualify for participation in the study, potential participants must meet the following eligibility inclusion criteria:

1. Have a history of autologous or allogeneic HSCT,
2. Be in at least partial remission and not on active treatment (maintenance chemotherapy is ok),
3. Have less than severe graft-versus-host-disease (GVHD)
4. 1 to 5 years post-HSCT,
5. Age 21 or older,
6. English language proficient
7. Able to provide informed consent
8. Endorse subjective cognitive impairment.

Potential participants will not be allowed to participate in the study if they meet any of the following exclusion criteria:

1. Being treated for, or been diagnosed with or suspected neurological, psychiatric (including bipolar disorder or mania), or medical condition that might impair cognitive functioning (other than those caused by the cancer or its treatment),
2. Visual, hearing, or physical impairment sufficient to interfere with cognitive testing or participation,
3. Have a history of whole brain irradiation or surgery,
4. Active diagnosis of autoimmune and/or inflammatory disorder or disorders that may influence immune processes,
5. Have a history of severe graft-versus-host-disease
6. History of systematic light exposure treatment,
7. Diagnosed sleep apnea or narcolepsy,
8. Use of photosensitizing medications (including antibiotics that render participants photosensitive),
9. Plan to travel across meridians during the study,
10. Work night, early morning, or swing shifts,

PROTOCOL TITLE: Treating cognitive impairments in cancer patients via systematic light exposure

11. Adults unable to consent, individuals who are not yet adults, pregnant women and prisoners will be excluded from the study.
12. History of eye disease including, but not limited to, macular degeneration.
13. Undergone laser corrective eye surgery in the past 30 days.

The excluded conditions have been chosen due to their known impact on cognitive function, the biomarkers to be studied, or are contraindications for light treatment.

4.0 Study-Wide Number of Subjects

Eighty autologous and allogeneic HSCT survivors will be recruited at Northwestern University, Feinberg School of Medicine, Department of Medical Social Sciences from Northwestern Memorial Hospital (NMH) and Robert H. Lurie Comprehensive Cancer Center (RHLCCC).

5.0 Study Timelines

5.1 The duration of an individual subject's participation in the study is 13 to 15 weeks depending on how quickly they send back the equipment. The duration anticipated to enroll all study subjects is 4 years. The estimated date for the investigators to complete this study's primary analyses is 5 years.

6.0 Study Endpoints

6.1 The primary endpoints in the proposed study are: 1) the level of cognitive functioning (as measured by the neuropsychological tests and self-reported cognitive functioning using the PAOFLI)

Secondary endpoints are: 1) Circadian activity rhythms using an actigraph (a small device similar in size to a watch that measures sleep and wake activity); 2) The Pittsburgh Sleep Quality Index; 3) the FACIT Fatigue Scale; 4) Quality of Life measured by the SF-36 scale; 5) a Credibility/Expectancy Questionnaire; 6) levels of Inflammatory Immune Markers; 7) the amount of time that the light boxes are used; 8) treatment satisfaction using the FACIT-TS-G scale; 9) depressed mood as measured by the CES-D; and 10) neurobehavioral functioning as measured by the Frontal Systems Behavior Scale.

6.2 With regard to safety endpoints, there are no known risks associated with the use of the light boxes in the treatment of cognitive impairments. However, we will monitor those who decide to cease treatment because they find the treatment approach unacceptable along with their concerns regarding treatment.

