- 5) **Cognitive Screening (Screening):** Participants will be asked whether they have concerns about their cognition by asking a question derived from the two cognitive questions on the

PROTOCOL TITLE: Treating cognitive impairments in cancer patients via systematic light exposure

European Organization for Research and Treatment of Cancer Quality of Life Questionnaire (EORTC QLQ C-30).

- 6) **Neuropsychologically-assessed Cognitive Functioning (Times 1, 3, and 4):** Standardized neuropsychological tests will be used to evaluate multiple cognitive domains. They include all of the tests recommended by the International Cognition and Cancer Taskforce in their Lancet article⁶ chosen due to their frequent use in CRCI assessment and appropriateness for repeat assessments over time: a) Premorbid Intellectual Function will be assessed using the Wechsler Test of Adult Reading and the Vocabulary subtest of the Wechsler Adult Intelligence Scale - 4th Ed. (WAIS-IV) at Baseline only; b) Psychomotor vigilance will be assessed with the Psychomotor Vigilance Task; c) Attention will be assessed with the Digit Span subtest of the WAIS-IV;⁹⁹ d) Visual motor performance will be assessed with the Grooved Pegboard Test and Block Design subtest of the WAIS-IV; e) Visuospatial ability will be assessed with the Rey Complex Figure Test. f) Sustained attention and vigilance will be assessed with the Conners Continuous Performance Test 3rd Edition will be used to assess sustained attention and vigilance; g) Information processing will be assessed with Trail-Making Test A.¹⁰⁰ h) Processing speed will be measured with the Coding subtest of the WAIS-IV; i) Verbal fluency will be assessed with the Verbal Fluency subtest of the Delis-Kaplan Executive Function System (D-KEFS). j) Verbal learning and Memory will be assessed with the Hopkins Verbal Learning Test - Revised.¹⁰² k) Visual learning and memory will be assessed with the Brief Visuospatial Memory Test – Revised. l) Executive Function will be assessed with Trail-Making Test B¹⁰⁰ and the Paced Auditory Serial Addition Task¹⁰³ and the Stroop Color and Word Test.

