- 7) **Subjective Cognitive Function (Times 1, 2, 3, and 4):** The Cognitive Failures Questionnaire is a 25-item self-report measure of cognitive difficulties in everyday life using a 5-point Likert scale. Its reliability and validity are well-documented. Those who score ≥ 43 are deemed to have clinically significant impairment. This measure has been used widely in the measurement of cognitive assessment, including for cancer-related cognitive impairment (e.g., Calvio, Peugeot, Bruns, Todd, & Beuerstein, 2010; Scherling, Collins, MacKenzie, Lepage, Bielajew, & Smith, 2012). Patient Assessment of Own Functioning Inventory – a 33-item self-report measure of a patient's self-perceptions regarding their functioning in everyday tasks and activities.
- 8) **Neurobehavioral functioning (Times 1, 2, 3, and 4):** The Frontal Systems Behavior Scale is a reliable and valid measure of neurobehavioral functioning (Grace & Malloy, 2001)
- 9) **Sleep Quality (Times 1, 2, 3 and 4):** The Pittsburgh Sleep Quality Index consists of 19 self-rated items (35). Scale reliability is excellent using both an internal consistency criterion (Cronbach's alpha = 0.83) and test-retest reliability ($r = 0.85$). The validity of the instrument is based on its ability to discriminate patients (those having either sleep problems and/or depressive symptoms) from controls (healthy participants without sleep complaints).
- 10) **Chronotype (Time 1):** The Morningness-Eveningness Questionnaire: A reduced scale (MEQr) will be used to collect data on baseline circadian predispositions (Horne & Ostberg, 1976; Adan & Almirall, 1991). It is a 5-item self-rated survey designed to measure whether a person's peak alertness is in the morning or evening. This measure takes approximately 1 minutes to complete.
- 11) **Physical health (Time 1):** Physical health measures will be included as covariates in data analyses as they have been shown to be associated with fatigue, sleep, depressed

PROTOCOL TITLE: Treating cognitive impairments in cancer patients via systematic light exposure

mood, and cognition.⁵⁷⁻⁶⁶ We will include Body Mass Index (a measure of adiposity) calculated by dividing a participant's weight by the square of their height. The World Health Organisation classifies a body mass index of 25-29.9 as overweight, 30-34.9 as obese class I, 35-39.9 as obese class II, and ≥ 40 as obese class III.

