patients used the light box about 50% of the required days. This usage frequency was sufficient for cognitive improvement to occur in the BWL group. A 50% level of adherence will be considered acceptable in this study. Acceptability: As recommended in the literature, in addition to accrual rates, we will assess acceptability by evaluating participants' comments about the intervention after they have had experience with it.¹¹³ Finally, a comparison of the BWL and DRL on the FACIT-TS-G will be conducted using t-tests. Significant differences in favor of the BWL condition are expected.

Aim 2: Examine whether BWL compared with DRL among HSCT survivors suffering from cognitive impairment yields significant improvements in cognitive functioning. We will examine the cognitive functioning subscales and composite scores in separate analyses. Linear mixed model analysis with repeated measures will be conducted using the SAS procedure MIXED.

Contrasts will compare groups across assessments. The linear mixed model approach has a range of choices for the error variance/covariance structure and accommodates missing data thus protecting against a "completers only" bias. Since multiple outcomes will be correlated with one another, *p*-values for significance will be Sidak-adjusted for multiple comparisons. If there is variation in light box utilization, we will use duration time as a predictor of the outcome measures as in Aim 1. No pre-intervention bias favoring BWL over DRL is anticipated. However, we will test this assumption by crossing expectancy with the treatment condition. This interaction is not expected to be significant. These results will determine preliminary efficacy and sustainability of the intervention.

Power: Based on [name]'s pilot study with 10 breast cancer patients, the effect size indicated that we would need a sample size of 19 to achieve power at 0.80. However, the sample size is likely too small to provide reliable estimates of improvement in cognitive functioning. One of the main aims is to determine preliminary efficacy of the intervention in preparation for a larger scale trial. For a total sample of 80, we calculated the mean difference between the two treatment arms for the Neurocognitive (composite) Index and assumed a repeated measures design with an autoregressive lag 1 error structure and autocorrelation of 0.60. The difference able to be detected with power equal to 0.80 and alpha = 0.05, is 0.209.

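### The primary cognitive endpoint joins 14 repeated tests and the PAOFLI without naming the deciding measure, time point or success rule, and the power statement covers only one unadjusted composite

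*Combined protocol and SAP*

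**What the plan says.** Section 6.1 gives one numbered primary item: "the level of cognitive functioning (as measured by the neuropsychological tests and self-reported cognitive functioning using the PAOFLI". It names no lead measure, time point or success rule.

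Section 7.3, item 6, describes the performance battery, scheduled as "Neuropsychologically-assessed Cognitive Functioning (Times 1, 3, and 4". It names 16 tests, of which two premorbid measures are baseline only. Item 7 schedules self-report differently: "Subjective Cognitive Function (Times 1, 2, 3, and 4". It also adds a second self-report scale, the Cognitive Failures Questionnaire, which 6.1 does not mention.

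Section 9.1, Aim 2, states: "We will examine the cognitive functioning subscales and composite scores in separate analyses". The model is a linear mixed model with group contrasts across assessments. Because the outcomes are correlated, p-values are to be Sidak-adjusted, but the outcomes in the family are neither listed nor counted. The paragraph ends: "These results will determine preliminary efficacy and sustainability of the intervention".

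The power text, in 9.1 and again in 9.2, singles out one outcome: "we calculated the mean difference between the two treatment arms for the Neurocognitive (composite) Index". For 80 participants it gives a detectable difference of 0.209 at power 0.80 and alpha 0.05. The component tests and scoring of that index are not given, and neither 6.1 nor the Aim 2 analysis text names it as primary.

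**The concern.** Performance tests and self-report measure different constructs and can disagree. If they do, the plan does not say what the trial has found. A null composite with a positive PAOFLI, the reverse, or one subscale that survives adjustment could each be presented as the answer to Aim 2.

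The Sidak adjustment limits false positives across the outcomes it covers. It does not say which of them answers the question.

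The analysis and the power statement also do not match. The sample size is justified for one composite at the full 0.05, whereas the analysis tests several outcomes at a smaller adjusted level. The quoted 80% power therefore does not describe the planned test.

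**Working it through.** **Inputs from the document.** 80 participants, 40 per arm; alpha 0.05; power 0.80; difference 0.209; autoregressive lag 1 structure with correlation 0.60 (9.1 and 9.2). Section 7.3, item 6: 16 tests − 2 baseline-only = 14 repeated tests, with Trail-Making A and B counted separately.

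**Not in the document, so assumed or varied.** Sidedness (two-sided assumed), the SD of the index, the contrast, the Sidak family size, power for the PAOFLI, and the correlation between the two instruments' test statistics.

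**Step 1: the plan's own figure.** Detectable difference = (1.960 + 0.842) × SD × √(2v/40), where v is the variance factor of the contrast.

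| Contrast | v | Difference at SD = 1 | SD that would give 0.209 |
|---|---|---|---|
| Single time point | 1 | 0.626 | 0.33 |
| Mean of three assessments | (3 + 4×0.60 + 2×0.36)/9 = 0.68 | 0.517 | 0.40 |
| Change between adjacent assessments | 2(1 − 0.60) = 0.80 | 0.560 | 0.37 |
| Baseline-adjusted, one later assessment | 1 − 0.60² = 0.64 | 0.501 | 0.42 |

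The 0.209 can be neither confirmed nor refuted, because the SD and the contrast are not stated. It depends on a choice of contrast that the plan does not make.

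**Step 2: effect of the planned Sidak adjustment.** Per-test level = 1 − 0.95^(1/k). Power at 0.209 = Φ(2.802 − z), where z is the two-sided critical value at that level. The missing SD cancels.

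| k | Level | z | Power at 0.209 | Difference detectable with 80% power |
|---|---|---|---|---|
| 1 | 0.0500 | 1.960 | 80% | 0.209 |
| 2 (composite, PAOFLI) | 0.0253 | 2.236 | Φ(0.565) = 71% | 0.230 |
| 15 (14 tests, PAOFLI) | 0.0034 | 2.928 | Φ(−0.126) = 45% | 0.281 |

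Counting the composite itself as a sixteenth outcome gives 44%. Taking 15 outcomes at two post-baseline times (k = 30) gives 37%.

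**Step 3: how often the instruments would split.** Take two normal test statistics, each with mean 2.802 (80% power at unadjusted 0.05), with correlation r. At r = 0, both succeed in 0.80² = 64% of trials and at least one in 1 − 0.20² = 96%, so exactly one succeeds in 32%. The other rows come from the bivariate normal distribution.

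| r | Both | At least one | Exactly one | Exactly one, Sidak k = 2 |
|---|---|---|---|---|
| 0 | 64% | 96% | 32% | 2 × 0.714 × 0.286 = 41% |
| 0.3 | 67% | 93% | 27% | about 33% |
| 0.5 | 69% | 91% | 23% | 28% |

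At r = 0.3 and unadjusted 0.05, a rule requiring both and a rule accepting either differ by about 27 percentage points in the chance of success. The plan states neither rule.

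**The case against.** The best defence is that this is an exploratory study. Feasibility is Aim 1, efficacy is called preliminary, and the outcomes, the model and the type of adjustment are all specified in advance. The power text implies that the composite leads. Any two endpoints can disagree, so the split figures measure disagreement, not error. All of this is fair and limits the severity. It does not supply a lead measure, a time point or a both/either rule, and 6.1 still makes cognition the only primary endpoint.

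Three stronger readings are tempting, but the documents do not support them.

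- **Inflated false-positive rate.** A reader might infer that two primaries at 0.05 nearly double alpha (either-wins rate 9.8% at correlation 0). But the Sidak sentence refers to multiple outcomes generally, and 6.1 counts the PAOFLI as cognitive functioning, so the natural reading puts it inside the family. With Sidak for two, the rate is 4.4% to 5.0% for correlations from 0.7 to 0.
- **A go/no-go decision.** A reader might infer that the Aim 2 result decides whether a large trial is prepared. Section 1.1 says only that efficacy is assessed in preparation for one. No decision rule is stated.
- **Expectation bias in self-report.** Participants see their light, but 7.1.1 has them told only that two wavelengths are being tested. Section 7.3 measures credibility and expectancy, and 9.1 tests expectancy crossed with treatment. The point here does not rest on this argument.

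Ranking the composite above self-report is also a judgement, since eligibility under 3.2 requires only subjective impairment. The essential step is to make and record the choice.

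**Conclusion.** The concern holds as a gap in the definition of the primary efficacy test and a mismatch between that test and its power statement. The plan should be changed, although an exploratory trial does not stand or fall on it.

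Power at the stated 0.209 is about 71% if the Sidak family has two outcomes and 45% if it has 15, against the quoted 80%. These figures rest on assumed family sizes and a two-sided test; they do not need the missing SD. The chance that exactly one instrument is significant is about 23% to 32% at unadjusted 0.05 and 28% to 41% with Sidak for two. Those figures assume that each instrument has 80% power at 0.05 and that the correlation lies between 0.5 and 0; the document gives neither. It would go too far to say that the efficacy answer will be picked after the data are seen. The supported statement is that the plan does not prevent that.

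**What to change.** In 6.1 and 9.1 (Aim 2), with 9.2 brought into line:

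1. Name the BWL versus DRL contrast on the Neurocognitive composite as the single primary efficacy test at two-sided 0.05. Fix its component tests and scoring before any unblinded analysis; without that, the choice stays open.
2. Name one contrast from the repeated-measures model, for example the baseline-adjusted difference at Time 3. The documents do not dictate Time 3, but it is the end of treatment and both instruments are collected then.
3. Restate the detectable difference for that contrast, with its SD.
4. Test the PAOFLI next, in fixed sequence, and claim it only if the composite is significant.
5. Report the subscales and the Cognitive Failures Questionnaire as supportive, with the planned Sidak adjustment over a listed family. Use Time 4 for the statement on sustainability.

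The cost is a few sentences, with no new data, visits or participants. There are two downsides. A positive PAOFLI or a single positive subscale could no longer establish efficacy alone. The restated detectable difference may also be less favourable than 0.209.
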